- **Moderate:** A type of AE that is usually alleviated with additional specific therapeutic intervention. The event interferes with usual activities of daily living, causing discomfort but poses no significant or permanent risk of harm to the patient.
- **Severe:** A type of AE that interrupts usual activities of daily living, or significantly affects clinical status, or may require intensive therapeutic intervention.

A "severe" reaction does not necessarily deem the AE as "serious," and an SAE may not be "severe" in nature.

Causality Relationship to IMP

Insulin (insulin lispro, Lilly Humalog), glucagon (glucagon for injection, Eli Lilly), and ZP4207 are all regarded as IMP.

The causality of each AE should be assessed by the Investigator according to the following classification:

- **Related:** Good reason and sufficient documentation to assume a causal relationship.
- **Not related:** No relationship to trial product can be established.

Outcome of an Adverse Event

The outcome of all AEs must be assessed by the Investigator and documented by his/her staff. The following definitions should be used:

- **Recovered/resolved:** The patient has fully recovered, or by medical or surgical treatment the condition has returned to the level observed at the first trial-related activity from Visit 3.
- **Recovering/resolving:** The condition is improving and the patient is expected to recover from the event. This term is only applicable if the patient has completed the trial.

Clinical Trial Protocol
ZP4207-16051

Version number: 6.0
Amendment 5.0
Date: 09 September 2016

- **Recovered/resolved with sequelae:** The patient has recovered from the condition, but with lasting effect due to a disease, injury, treatment, or procedure. If a sequela meets an SAE criterion, the AE must be reported as an SAE.
- **Not recovered/not resolved:** The condition of the patient has not improved and the symptoms are unchanged, or the outcome is not known.
- **Fatal:** This term is only applicable if the patient died from a condition related to the reported AE. Outcomes of other reported AEs in a patient before he/she died should be assessed as “recovered/resolved,” “recovering/resolving,” “recovered/resolved with sequelae,” or “not recovered/not resolved.” An AE with a fatal outcome must be reported as an SAE.
- **Unknown:** This term is only applicable if the patient is lost to follow-up.

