10.2 Serious Adverse Events

An SAE is any untoward medical occurrence that at any dose:

- Results in death
- Is life-threatening
- Requires inpatient hospitalization or prolongation of existing hospitalization
- Results in persistent or significant disability or incapacity
- Is a congenital anomaly or birth defect
- Medically important

Medical judgement must be exercised in deciding whether an AE is believed to be “medically important.” Medically important events may not be immediately life-threatening or result in death or hospitalization, but may jeopardize the patient or may require intervention to prevent 1 of the other outcomes listed in the [definition](#) above.

Suspected Unexpected Serious Adverse Reactions (SUSAR)

A SUSAR is an AE fulfilling 1 of the criteria of seriousness and being assessed as related to an IMP, the nature or severity of which is not consistent with the applicable reference document (e.g., ZP4207 IB or package leaflet/SPC for an approved product).

Unanticipated Adverse Device Effect (UADE)

A UADE is any serious adverse effect on health or safety, any life-threatening problem or death caused by, or associated with a device, if that effect, problem, or death was not previously identified in nature, severity, or degree of incidence in the application; or any other unanticipated serious problem associated with a device that relates to the rights, safety, or welfare of patients.

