The Investigator must report initial information in writing on the SAE Form for all SAEs to the Sponsor's responsible pharmacovigilance unit (here: Lindeq) immediately (within 24 hours) after obtaining knowledge about the event.

Name: [REDACTED]
Company: Lindeq
Address: [name]
Tel: [REDACTED]
Fax: [REDACTED]
Mobile: [REDACTED]
E-mail: [contact]

In addition and meeting the same timeline, Investigators must report all SAEs to Zealand Pharma A/S by forwarding the SAE Form electronically within 24 hours of obtaining knowledge of the event to the representatives of Zealand Pharma A/S.

Clinical Trial Protocol
ZP4207-16051

Version number: 6.0
Amendment 5.0
Date: 09 September 2016

Names: [REDACTED] and [REDACTED]
Address: [name]
Tel: [REDACTED]
E-mails: [REDACTED]

It is the responsibility of Lindeq to report all SUSARs that occur in this trial to the Competent Authorities and to the Investigators. It is the responsibility of the Investigators to report the SUSARs to the IRBs in accordance with the local requirements in force and the International Conference on Harmonisation (ICH) guideline for Good Clinical Practice (GCP). The trial monitor must be informed accordingly.

It is the responsibility of Lindeq to report all serious adverse reactions on insulin lispro and glucagon for injection to the Eli Lilly Pharmacovigilance department within 5 days.

It is the responsibility of the Investigators to report all UADEs to Beta Bionics within 24 hours of the time they are detected. It is the responsibility of the Investigators to report all UADEs to the IRB in accordance with the local requirements in force and the ICH GCP. It is the responsibility of Beta Bionics to report all UADEs to the Competent Authorities.

All device deficiencies should be documented and should be reported to Beta Bionics within 24 hours. Device deficiencies are inadequacies of a medical device with respect to its identity, quality, durability, reliability, safety, or performance.

Name: [REDACTED]
Company: Beta Bionics, Inc.
Address: [name]
[name], United States
Tel: [REDACTED]
E-mail: [REDACTED]

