10.6 Safety Monitoring

10.6.1 Data and Safety Monitoring Board

An external DSMB will oversee the conduct of the trial, as set forth in the DSMB Charter. Additionally, the DSMB will be informed in the event of any serious and unexpected AEs. The DSMB will be informed if there are any changes to the trial protocol that could significantly impact the safety or scientific validity of the trial. A final DSMB meeting will convene after the completion of the trial.

The participation of individual patients will be discontinued if they experience:

- Seizure or unconsciousness associated with hypoglycemia and associated with participation in the trial
- Persistent nausea and vomiting thought to be related to glucagon dosing associated with participation in the trial
- Hospitalization associated with participation in the trial
- Pregnancy
- Diabetic ketoacidosis

If more than 1 patient must be withdrawn from the trial for these reasons, the trial will stop and a vote of the DSMB will be required to restart it. All AEs that are serious and unexpected but related will be reported to the DSMB within 5 working days.

Clinical Trial Protocol
ZP4207-16051

Version number: 6.0
Amendment 5.0
Date: 09 September 2016

Note that patients may discontinue participation at any time. Patients may be removed from the trial for other reasons, for instance, failure to comply with trial procedures or intercurrent illness that is unrelated to the BP but that precludes safe participation. Discontinuation of participation for these reasons will not contribute to a decision to discontinue the trial.

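### The causality definitions in protocol section 10.1.3 put a reasonable but thinly documented suspicion under Not related, so such a serious, unexpected event may escape SUSAR classification and the 5-working-day DSMB deadline

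*Protocol*

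**What the plan says.** Section 10.1.3 (protocol version 6.0) gives the causality judgement to the Investigator: "The causality of each AE should be assessed by the Investigator according to the following classification". There are two levels:

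- *Related*: "Good reason and sufficient documentation to assume a causal relationship".
- *Not related*: "No relationship to trial product can be established".

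No level exists for a possible or probable relation. Section 10.3 asks for five separate ratings per AE: ZP4207, insulin, glucagon, the device and procedures.

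Two expedited routes use the rating. Section 10.2 makes a serious event a SUSAR only on "being assessed as related to an IMP, the nature or severity of which is not consistent with the applicable reference document", and section 10.3 attaches the onward duty: "It is the responsibility of Lindeq to report all SUSARs that occur in this trial to the Competent Authorities and to the Investigators". Section 10.6.1 states: "All AEs that are serious and unexpected but related will be reported to the DSMB within 5 working days".

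Section 10.6.1 also has a DSMB sentence with no causality condition and no deadline: "Additionally, the DSMB will be informed in the event of any serious and unexpected AEs".

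**The concern.** The definition of *Related* joins two requirements with an and: a good reason, and enough documentation. The definition of *Not related* covers whatever cannot be established. An Investigator who suspects a product but lacks documentation has only one category that fits, and it is *Not related*. Doubt is therefore resolved away from the product. For safety reporting it should be resolved the other way.

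This sits badly with other thresholds in the same protocol. The SUSAR category is named for suspicion, yet its operative condition is a rating that needs more than suspicion. In section 10.2 a device effect can qualify as a UADE by association with the device. In section 10.6.1 a patient is discontinued for persistent nausea and vomiting if these are merely believed to come from glucagon dosing. The drug causality scale is stricter than both.

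Attribution can also be hard in this design. Insulin and either glucagon or ZP4207 are given together through a device, and the washout may be as short as 24 hours. Follow-up runs to 25 ± 4 days after Visit 4, so up to 25 + 4 = 29 days. By then a patient who completed both visits has received all three products. For a late event, enough documentation to assign it to ZP4207 may not be obtainable even when a relation is reasonably possible.

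At stake is whether such an event reaches the Competent Authorities and the other recipients of SUSARs, how fast it reaches the DSMB, and how it is labelled in the listing.

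**Working it through.** No arithmetic applies. The check follows one hypothetical event through the text: serious, unexpected, with a plausible link to ZP4207 that is not well documented.

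**Step 1: the rating (section 10.1.3).** The event meets the first half of *Related* (good reason) but not the second (sufficient documentation). No relation has been established, so it meets *Not related*. Read literally, the event is rated *Not related*.

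**Step 2: the routes that follow.**

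| Route | Section | Depends on a related rating? | Deadline stated | This event |
|---|---|---|---|---|
| SAE report to the Sponsor | 10.3 | No | 24 hours | Reported |
| SAE Form to the pharmacovigilance unit and Sponsor representatives | 10.3 | No | 24 hours | Reported |
| AE report to the IRB | 10.3 | No | Prompt, per local requirements | Reported |
| DSMB informed of serious, unexpected AEs | 10.6.1 | No | None | Informed, timing open |
| Sponsor's Safety Committee review of AEs | 10.6.2 | No | At its meetings | Reviewed |
| SUSAR report to Competent Authorities and Investigators | 10.2, 10.3 | Yes | None in that sentence | May not qualify |
| DSMB report of serious, unexpected, related AEs | 10.6.1 | Yes | 5 working days | Deadline does not apply |
| Individual AE listing | 11.2.1 | Shows the rating | n/a | Shown as not related |

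**Step 3: the two DSMB sentences side by side.** One covers every serious and unexpected AE and gives no time limit. The other gives 5 working days but only for related ones. Together they leave a serious, unexpected event rated *Not related* within the DSMB's remit but without a clock. A reader cannot tell whether the second sentence adds a deadline to a subset or was meant to define what is reported.

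**Step 4: can the rating be raised later?** Section 10.2 does not say whose assessment counts for SUSAR status. Section 10.1.3 gives the assessment to the Investigator. The protocol text available for this review (part 2 of 3 of the document) describes no separate Sponsor assessment that could override a *Not related* rating.

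**The case against.** Much can be said for the protocol as it stands.

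- **The event does not disappear.** Five of the routes above carry it whatever the causality, two of them within 24 hours. Section 10.3 also requires FDA reporting to follow the Code of Federal Regulations. This stands, and it limits the point to SUSAR classification, the DSMB deadline and the listing.
- **The definition asks for grounds to assume causality, not for proof.** This stands too. A well-documented suspicion can be rated *Related*, so only the thinly documented ones are affected. Two levels are not themselves a fault; the definitions are.
- **Treatment is closely observed.** An RN or MD is present throughout, nausea, pain and site reactions are scored hourly, and plasma sampling is at least hourly. Documentation for the expected events on treatment days should be good. This is less help for events during follow-up.
- **A Sponsor assessment may be described elsewhere.** Its absence from the text reviewed does not show that none exists.

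A reader might infer more than the documents support: that events will be missed altogether, that most AEs will be of the uncertain kind, or that the count of ZP4207-related events is biased toward zero. The first is contradicted by the routes that do not depend on causality. The second has no figure behind it. The third supposes a count that the protocol does not plan: the primary endpoint in section 8.1 is number and type of AEs, and the conditional summary table in section 11.2.1 is by system organ class and treatment period. Relationship appears only in the listing of individual events.

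**Conclusion.** The concern holds in this limited form. If the definitions are followed exactly, a serious, unexpected event with a reasonable but insufficiently documented link to a product is rated *Not related*. It may then escape SUSAR classification, loses the 5-working-day DSMB deadline, and is listed as not related. It still reaches the Sponsor and the pharmacovigilance unit within 24 hours, and the DSMB at an unstated time.

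The size of the effect cannot be estimated. The documents give no expected number of serious events and no indication of what share would be uncertain. The number affected could be zero in a trial that expects 20 to 24 randomized patients. The conclusion assumes that Investigators apply the definitions as worded and that no Sponsor assessment, in text not reviewed, governs SUSAR status. An Investigator who rates cautiously would avoid the problem, but nothing in section 10.1.3 tells them to.

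This is a fault of wording in a safety rule, cheap to correct and worth correcting.

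**What to change.** 1. In section 10.1.3, define *Related* as a reasonable possibility of a causal relationship to the product, and *Not related* as no reasonable possibility. The categories are then exclusive and doubt goes to *Related*. Do not add a more likely alternative cause as a ground for *Not related*: an event can have one and still be reasonably possible, so the categories would overlap.
2. Keep the separate ratings for ZP4207, insulin, glucagon, device and procedures in section 10.3.
3. In section 10.6.1, reconcile the two DSMB sentences: say whether the report covers all serious and unexpected AEs or only related ones, and give one deadline. Version 5.0 repeats the 5-working-day sentence in section 4.4; if version 6.0 does too, change both.
4. If the Sponsor makes its own causality assessment, say so in section 10.2 and state which rating governs SUSAR status.

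The cost is wording in the protocol, the eCRF and the safety documents. The downside is that somewhat more events will be rated related and sent through the expedited routes.

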10.2 Serious Adverse Events

An SAE is any untoward medical occurrence that at any dose:

- Results in death
- Is life-threatening
- Requires inpatient hospitalization or prolongation of existing hospitalization
- Results in persistent or significant disability or incapacity
- Is a congenital anomaly or birth defect
- Medically important

Medical judgement must be exercised in deciding whether an AE is believed to be “medically important.” Medically important events may not be immediately life-threatening or result in death or hospitalization, but may jeopardize the patient or may require intervention to prevent 1 of the other outcomes listed in the [definition](#) above.

Suspected Unexpected Serious Adverse Reactions (SUSAR)

A SUSAR is an AE fulfilling 1 of the criteria of seriousness and being assessed as related to an IMP, the nature or severity of which is not consistent with the applicable reference document (e.g., ZP4207 IB or package leaflet/SPC for an approved product).

Unanticipated Adverse Device Effect (UADE)

A UADE is any serious adverse effect on health or safety, any life-threatening problem or death caused by, or associated with a device, if that effect, problem, or death was not previously identified in nature, severity, or degree of incidence in the application; or any other unanticipated serious problem associated with a device that relates to the rights, safety, or welfare of patients.

10.3 Adverse Event Reporting – Procedures for Investigators

The Principal Investigator and co-investigators will review any AEs and report any SAEs to the Sponsor as soon as possible and within 24 hours of obtaining knowledge of the event. The Principal Investigator and co-investigators will promptly report AEs to the Partner’s Institutional Review Board (IRB) and to the BU IRB (unless oversight is ceded by the BU IRB to the Partners IRB), in accordance with local requirements.

[name] is the Sponsor of the Investigational Device Exception for the BP and Zealand Pharma A/S is the Sponsor of the IND for ZP4207.

Clinical Trial Protocol
ZP4207-16051

Version number: 6.0
Amendment 5.0
Date: 09 September 2016

Reports of AEs will be submitted to the FDA in compliance with the terms of the Code of Federal Regulations.

All events meeting the definition of an AE must be collected and reported from the first trial-related activity from Visit 3 until the end of the post-treatment follow-up period. At each contact with the site (visit or telephone, excluding safety visits, where the patient is not seeing the Investigator or staff [e.g., visits to the laboratory], the patient must be asked about AEs. All AEs, either observed by the Investigator or reported by the patient, must be recorded by the Investigator and evaluated.

The Investigator should record the diagnosis, if possible. If no diagnosis can be made, the Investigator should record each sign and symptom as individual AEs. All AEs must be recorded by the Investigator. One single AE Form must be used per AE from start to resolution. For SAEs, the SAE Form must also be completed.

AE information should include the following:

- Patient identification number on all pages
- Date and time of treatment start
- Date and time of onset and date of outcome
- Date and time of Investigator's first information on the (S)AE
- Seriousness
- Severity
- Causal relationship with IMP ZP4207
- Causal relationship with IMP insulin
- Causal relationship with IMP glucagon
- Causal relationship with medical device
- Causal relationship with procedures
- Interruption or withdrawal of treatment with IMP or medical device and other measures taken
- Outcome

All AEs are coded; details are described in the trial specific Data Management Plan.

The Investigator must report initial information in writing on the SAE Form for all SAEs to the Sponsor's responsible pharmacovigilance unit (here: Lindeq) immediately (within 24 hours) after obtaining knowledge about the event.

Name: [REDACTED]
Company: Lindeq
Address: [name]
Tel: [REDACTED]
Fax: [REDACTED]
Mobile: [REDACTED]
E-mail: [contact]

In addition and meeting the same timeline, Investigators must report all SAEs to Zealand Pharma A/S by forwarding the SAE Form electronically within 24 hours of obtaining knowledge of the event to the representatives of Zealand Pharma A/S.

Clinical Trial Protocol
ZP4207-16051

Version number: 6.0
Amendment 5.0
Date: 09 September 2016

Names: [REDACTED] and [REDACTED]
Address: [name]
Tel: [REDACTED]
E-mails: [REDACTED]

It is the responsibility of Lindeq to report all SUSARs that occur in this trial to the Competent Authorities and to the Investigators. It is the responsibility of the Investigators to report the SUSARs to the IRBs in accordance with the local requirements in force and the International Conference on Harmonisation (ICH) guideline for Good Clinical Practice (GCP). The trial monitor must be informed accordingly.

It is the responsibility of Lindeq to report all serious adverse reactions on insulin lispro and glucagon for injection to the Eli Lilly Pharmacovigilance department within 5 days.

It is the responsibility of the Investigators to report all UADEs to Beta Bionics within 24 hours of the time they are detected. It is the responsibility of the Investigators to report all UADEs to the IRB in accordance with the local requirements in force and the ICH GCP. It is the responsibility of Beta Bionics to report all UADEs to the Competent Authorities.

All device deficiencies should be documented and should be reported to Beta Bionics within 24 hours. Device deficiencies are inadequacies of a medical device with respect to its identity, quality, durability, reliability, safety, or performance.

Name: [REDACTED]
Company: Beta Bionics, Inc.
Address: [name]
[name], United States
Tel: [REDACTED]
E-mail: [REDACTED]

10.4 Pregnancy Reporting

Female patients must be instructed to notify the Investigator immediately if they become pregnant or if they suspect to be pregnant during the trial. The Sponsor has a responsibility to monitor the outcome of all pregnancies reported during the clinical trial.

Male patients must be instructed to notify the Investigator immediately if their partner becomes pregnant or suspects to be pregnant. The Sponsor has a responsibility to monitor the outcome of all pregnancies reported during the clinical trial. During an information meeting at the trial site, the patient's partner will be fully informed by a physician of her participation in capturing the outcome data, and will be asked to provide her written consent.

The Investigator must report all information on pregnancies, including AEs in the patient/patient's partner, the fetus, and newborn infant/ toddler. The pregnancy report must be forwarded to the Sponsor preferably electronically as PDF or by fax.

The Investigator must follow the pregnancy until the pregnancy outcome and the newborn infant(s) until the age of 1 month. The Investigator must collect information on the pregnancy and pregnancy complications as well as the pregnancy outcome including the health of the newborn infant(s) on the pregnancy forms.

Clinical Trial Protocol
ZP4207-16051

Version number: 6.0
Amendment 5.0
Date: 09 September 2016

The following must be collected:

- Initial information of the pregnancy
- Information on the outcome of the pregnancy, including the health status of the newborn infant(s) at the age of 1 month
- All AEs in connection with the pregnancy and pregnancy outcome must be reported on the pregnancy forms. It must be clear in the description if the event occurs in the patient/patient's partner, the fetus, or the newborn infant.
- All SAEs in connection with the pregnancy and pregnancy outcome must be reported on the pregnancy forms following the same timelines as required for other SAEs. It must be clear in the description if the event occurs in the patient/patient's partner, the fetus, or the newborn infant.

The SAEs that must be reported include abnormal outcome – such as congenital anomalies, fetal death, and termination of pregnancy (spontaneous or elective abortion), including any anomalies of the fetus observed at gross examination or during autopsy – as well as other pregnancy complications (ectopic pregnancy) fulfilling the criteria of an SAE.

